18 Response will be assessed every cycle while on study drug treatment, and at study treatment discontinuation. Screening labs do not need to be repeated at C1D1 if they have been completed within 14 days. Assessment of response will include measurement of serum M-protein by electrophoresis, SFLC analysis, and IFE studies (see footnotes 10-12).

19 VTE assessment will be performed at each visit during study treatment and at study treatment discontinuation.

20 AEs will be assessed starting at baseline (C1D1). AEs that lead to study treatment discontinuation should be followed until resolution or stabilization. Serious adverse events (SAEs) will be assessed until 30 days after study treatment discontinuation.

21 Second primary malignancies will be monitored as events of interest and must be reported as SAEs regardless of the dose cohort the patient is in. This includes any second primary malignancy, regardless of causal relationship to study drug (ACY-1215, pomalidomide, dexamethasone), occurring at any time for the duration of the study, from the time of signing the informed consent up to the time all patients have been followed for at least 1 year post the 30 day discontinuation visit or have died. Events of second primary malignancy are to be reported using the SAE report form and must be considered an "Important Medical Event" even if no other serious criteria apply; these events must also be documented in the appropriate page(s) of the case report form (CRF) and patient's source documents. Documentation on the diagnosis of the second primary malignancy must be provided at the time of reporting as an SAE (e.g., any confirmatory histology or cytology results, X-rays, computed tomography [CT] scans, etc.).

22 ACY-1215 will be administered on Day 1 of each 28-day cycle. For patients enrolled in Dose Level 1, the starting dose of ACY-1215 will be 160 mg QD on Days 1-21 of a 28-day cycle. Patients enrolled in Dose Level 2 will receive 240 mg QD on Days 1-21 of each 28-day cycle. Patients enrolled in Dose Level 3 will receive 160 mg BID on Days 1-21 of each 28-day cycle. In the Phase 2 segment, the ACY-1215 dose and schedule is 160 mg PO QD on Days 1 to 21 of a 28-day cycle.

23 Pomalidomide will be administered 4 mg PO on Days 1-21 of each 28-day cycle.

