addition, all patients will be given aspirin 81 or 325 mg daily (commercial supply) as prophylactic anti-thrombotic treatment unless contraindicated. If aspirin is contraindicated, patients will receive another form of anti-thrombotic therapy according to hospital guidelines or physician preference. All patients will be monitored for signs and symptoms of venous thromboembolism (VTE) while on pomalidomide; diagnostic algorithms are provided (Appendix 9.1). The study will conclude 30 days after the last enrolled patient discontinues from the study due to disease progression or treatment discontinuation.

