Patients are to be evaluated for disease response after every cycle and at study treatment discontinuation, starting with Cycle 1. The severity of AEs will be graded according to the National Cancer Institute Common Terminology Criteria for Adverse Events (NCI CTCAE) Version 4.0 (Appendix 9.2). Patients who withdraw from the study are to be followed up either in person or by phone 30 days (± 3 days) after the last dose of study drug. If patients are treated with an alternate MM therapy before the 30 day visit, assessments for the 30 day visit should be performed prior to initiation of the alternate therapy. Upon discontinuation from study treatment for PD or any other reason, patients will be assessed 3 times per year (e.g., April, August, and December), for up to 5 years, for survival, subsequent anti-myeloma therapies, and monitoring of second primary malignancies as outlined in Table 1. Patients who discontinue study treatment due to reasons other than PD will also be followed for efficacy assessments (assessment of response, extramedullary plasmacytoma assessment, quantitative serum immunoglobulin levels, serum and urine protein electrophoresis of myeloma [M]-protein levels [SPEP, UPEP], serum and urine immunofixation [IFE] studies, and serum free light chain [SFLC] analysis) until PD, death, or initiation of an alternate MM therapy, whichever occurs first. Subsequent therapies should be collected until death or end of 1 year follow up period. Survival follow up may be done via phone. Serious adverse events (SAEs) will be collected from C1D1 through the first 30 days of follow-up. Females of childbearing potential (FCBP) with regular or no menstruation will be required to have a final pregnancy test at study treatment discontinuation, and at Day 28 following study treatment discontinuation. Females with irregular menstruation must have a pregnancy test at study treatment discontinuation, and at Day 14 and Day 28 following study treatment discontinuation.

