Safety is to be evaluated during the study by documentation of AEs, including SAEs, clinical laboratory tests (hematology, serum chemistry, and urinalysis), physical examinations, vital sign measurements, performance status, and 12-lead electrocardiograms (ECGs). All safety and efficacy laboratory tests will be analyzed by local laboratories. A central laboratory will analyze duplicate samples of serum immunoglobulin levels, SPEP and UPEP of M-protein levels, serum and urine IFE studies, and SFLC analysis. A bone marrow aspirate sample will be centrally analyzed for fluorescence *in situ* hybridization (FISH)/cytogenetics. Results from the central efficacy analysis will not be shared with sites.

Second primary malignancies will be monitored as events of interest and should be included as part of the assessment of AEs throughout the course of the study. Investigators are to report any second primary malignancies as SAEs regardless of causal relationship to study drugs, occurring at any time for the duration of the study, from the time of signing the informed consent up to the time all patients have been followed for at least 1 year from randomization or have died.

The anti-tumor activity of ACY-1215 in combination with pomalidomide and dexamethasone will be determined by assessment of disease response using the consensus recommendations based on the IMWG criteria, published by Rajkumar et al., in Blood in 2011, which includes the category of minimal response (MR) (as defined by European Group for Blood and Marrow Transplantation [EBMT] criteria) for relapsed refractory MM (Appendix 9.5,

Appendix 9.7).[50,53] In order to assess response, M-protein component is to be measured in serum and urine, FreeLite™ testing is to be performed and, as applicable, bone marrow aspirate and biopsies, and appropriate imaging studies (e.g., computed tomography [CT], MRI) are to be performed. Patients who are determined to have PD at any time are to be discontinued from the study.

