4.7. Patient Management

This study will be conducted on an outpatient basis.

Patients will be evaluated for study eligibility at screening, within 28 days before the first study drug dose. All patients must provide written informed consent before any samples are collected or evaluations are performed in this study. If patients have had recent scans, bone marrow biopsy, or blood test for other purposes prior to enrollment, these tests may be used for determination of eligibility if they were performed within the 28-day period before Baseline (C1D1, before study drug administration). Patients who are determined to be eligible will be enrolled in the study at Baseline. Patients will be evaluated at the study center on Days 1, 2, 8, 15, and 22 of Cycle 1. During Cycle 2, patients will be evaluated at the study center on Days 1 and 15. For all subsequent cycles, patients will be evaluated at the study center on Day 1. Patients who withdraw from the study are to be followed up either in person or by phone 30 days (\pm 3 days) after the last dose of study drug. If patients are treated with an alternate MM therapy before the 30 day visit, assessments for the 30 day visit should be performed prior to initiation of the alternate therapy.

Patients are to receive study treatment until development of PD or an unacceptable toxicity that cannot be managed by dose reduction alone precludes further treatment. Upon discontinuation from the study for PD or any other reason, patients will be assessed 3 times per year (e.g., April, August, and December), for up to 1 years for survival, subsequent anti-myeloma therapies, and monitoring of second primary malignancies as outlined in Table 1. SAEs will be collected from C1D1 through the first 30 days of follow-up. Subsequent therapies should be collected until death or end of the 1 year follow-up period. Survival follow up may be done via phone, when relevant. Patients who discontinue study treatment due to reasons other than PD will also be followed for efficacy assessments (see Section 6.2) until PD, death, or initiation of an alternate MM therapy, whichever occurs first.

Patients who have been contacted at least 3 times without success (at least 1 month apart) should be sent a certified letter. If no contact is established, the patient will be deemed lost to follow up. A similar process will be followed for patients being followed up by phone. All attempted contact should be documented in the patient's medical chart.

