6.1.8.3. Second Primary Malignancies

Second primary malignancies will be monitored as events of interest and must be reported as SAEs. This includes any second primary malignancy, regardless of causal relationship to study drug (ACY-1215, pomalidomide, dexamethasone), occurring at any time for the duration of the study, from the time of signing the informed consent up to the time all patients have been followed for at least 1 year from discontinuation or have died. Events of second primary malignancy are to be reported using the SAE report form and must be considered an "Important Medical Event" even if no other serious criteria apply; these events must also be documented in the appropriate page(s) of the eCRF and patient's source documents. Documentation on the diagnosis of the second primary malignancy must be provided at the time of reporting as an SAE (e.g., any confirmatory histology or cytology results, X-rays, CT scans, etc.).

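### Section 3.1 closes the study 30 days after the last enrolled patient discontinues, while second-malignancy reporting must run at least a year beyond discontinuation and other follow-up starts at that same event

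*Combined protocol and SAP*

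**What the plan says.** All of the following is current text, not the summaries of changes.

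- **Study end.** Section 3.1: "The study will conclude 30 days after the last enrolled patient discontinues from the study due to disease progression or treatment discontinuation".
- **Start of follow-up.** Section 4.7: "Upon discontinuation from the study for PD or any other reason, patients will be assessed 3 times per year". The length given there is up to 1 year. The synopsis, Table 1 footnote 3 and Section 6.2.7 give the same length.
- **Duration in Section 3.1.** Patients are assessed "for up to 5 years, for survival, subsequent anti-myeloma therapies, and monitoring of second primary malignancies as outlined in Table 1". Later in the same paragraph: "Subsequent therapies should be collected until death or end of 1 year follow up period".
- **Second primary malignancies.** Three sections set three starting points. Section 3.1 has reporting continue "up to the time all patients have been followed for at least 1 year from randomization or have died". Table 1 footnote 21 has it continue until all patients have been "followed for at least 1 year post the 30 day discontinuation visit or have died". Section 6.1.8.3 has it continue "up to the time all patients have been followed for at least 1 year from discontinuation or have died".
- **Addendum.** Section 7.5.3 prepares the addendum to the final analysis once every patient has withdrawn from the study, without defining withdrawal. Section 4.6 lists progressive disease among the reasons for withdrawal, and Section 3.1 says "Patients who withdraw from the study are to be followed up either in person or by phone 30 days" after the last dose.

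**The concern.** One event, discontinuation for progression or end of treatment, starts both a 30-day countdown to study closure and a follow-up window of about a year. For second malignancies the two cannot both be honoured unless the patients concerned die first, because footnote 21 and Section 6.1.8.3 set a minimum.

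What is at stake is late data. Second malignancies are designated events of interest, reportable as serious adverse events whatever their cause. Table 1 schedules survival status only at the three-times-a-year contacts, and Section 7.6.7 plans Kaplan-Meier curves and one-sample inference for overall survival. Patients who stop treatment for reasons other than progression are also to stay under efficacy assessment until progression, death or a new myeloma therapy (3.1, 6.2). For those who stop late, study end would cut that short. A data manager who took the Section 3.1 sentence as the closing date would lose part of all three.

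**Working it through.** The plan gives no calculated figure to reproduce here. The check is a day count using the protocol's own durations.

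**Inputs.** Study end is 30 days after the defining discontinuation (3.1). The second-malignancy minimum is 1 year from discontinuation (6.1.8.3), or 1 year from the 30-day visit (Table 1, footnote 21). Survival contacts come 3 times a year, about every 4 months (6.2.7), with a window of ±7 days (Table 1). A cycle is 28 days.

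**Reading A (assumption): the sentence means the last patient to discontinue.** Let day 0 be that discontinuation, and suppose the patient is alive.

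| Requirement | Earliest day it is met | Study end | Shortfall |
|---|---|---|---|
| 6.1.8.3 | 365 | 30 | 365 − 30 = 335 days |
| Footnote 21 | 30 + 365 = 395 | 30 | 395 − 30 = 365 days |

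The patient has 30/365 = 8% of the Section 6.1.8.3 minimum. A surviving patient who discontinued *d* days earlier has *d* + 30 days before study end. Such a patient meets Section 6.1.8.3 only if *d* ≥ 335, and footnote 21 only if *d* ≥ 365.

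For survival, contacts at 4-month spacing fall near days 122, 244 and 365. Even the earliest, taken 7 days early, is day 115, so none is reached by day 30. If contacts are instead fixed to calendar months, as in the protocol's April/August/December example, at most one can fall in the period. The chance of that is about 30/122 = 25%, or (30 + 14)/122 = 36% if the ±7-day window is used, assuming discontinuation is equally likely on any date. The 30-day visit does cover adverse events, second malignancies and subsequent therapies, but Table 1 does not schedule survival status there.

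**Reading B (literal): the last patient to enrol.** Study end then depends on one person's time on treatment. If that patient stops early, the study closes 30 days later whatever the status of earlier-enrolled patients, some of whom may still be on treatment. The documents give no time-on-treatment distribution, so no count can be attached.

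**The randomization anchor.** Sections 3.1 and 5.3.1 describe a single-arm study, so no such date exists. If it is read as first dose, the minimum second-malignancy follow-up after discontinuation is 365 minus time on treatment:

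| Time on treatment | 3.1 (read as first dose) | 6.1.8.3 | Footnote 21 |
|---|---|---|---|
| 6 cycles = 168 days | 365 − 168 = 197 | 365 | 395 |
| 12 cycles = 336 days | 365 − 336 = 29 | 365 | 395 |

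Meeting footnote 21 therefore also meets the other two, but Section 3.1 alone can be met much earlier.

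**The 5 years.** Section 3.1 says up to 5 years and refers to Table 1, whose footnote 3 says up to 1 year. The same paragraph later speaks of a 1-year period, and the synopsis and Sections 4.7 and 6.2.7 agree with 1 year. The stated rationale for Amendment 4 is a reduction from 5 years to 1 year after treatment discontinuation, so this looks like a leftover.

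**The case against.** The best defence has four parts.

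1. **Survival follow-up is a ceiling.** A reader might infer that a full year of survival follow-up is mandatory and that Section 3.1 breaches it. The sections say up to 1 year, so a shorter period does not strictly contradict them. This stands. The direct conflict is with second-malignancy reporting, which has a minimum.
2. **Nobody is told to stop.** The study-end sentence instructs no site to cease collection, and Section 3.1 sends sites to Table 1 for their visits. The protocol also allows for later activity: drug-related serious events beyond 30 days remain reportable (6.1.8), and follow-up of adverse events may outlast the study (6.1.8.5). It is therefore not established that data would be lost in practice. However, those provisions cover only drug-related late events and events already under way. They do not cover a new second malignancy irrespective of cause, or survival status.
3. **Discontinuing from the study could mean the end of follow-up.** The sentence itself ties it to progression or treatment discontinuation, so this reading fails.
4. **The secondary items are editorial.** The three second-malignancy anchors can be satisfied together, and the 5 years errs towards collecting too much. The addendum trigger can be read as the end of all participation, follow-up included, so it is ambiguous rather than shown to fire early. These points stand, and the items are treated here as wording defects only.

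**Conclusion.** Section 3.1 is wrong as written. Its study end cannot be reconciled with the second-malignancy minimum in footnote 21 and Section 6.1.8.3 unless the patients concerned die first. It also falls at the beginning, not the end, of survival and subsequent-therapy follow-up.

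The size depends on the reading. With the last patient to discontinue (assumed), study end comes 335 or 365 days before the second-malignancy window can close for that patient if alive. With the last patient to enrol, it could come while others are still on treatment, by an amount the documents do not allow one to calculate.

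A reader might infer bias in the efficacy result or damage to the main analysis. The documents do not support that: the primary endpoint, sample size and interim rules do not depend on study end, and overall survival is analysed but is not a listed endpoint in Section 2.2. Under the first reading, the triggers for the final analysis (7.5.2) and the Phase 2 safety analysis (7.6.6) are met no later than the last discontinuation, so both precede study end. Under the literal reading that ordering is not guaranteed, and nothing is claimed about it. The loss is confined to late second-malignancy, overall-survival and post-treatment efficacy data, with no estimate of how many patients are involved.

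**What to change.** Amend the wording as follows:

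- **3.1, study end:** define it as the date on which the last patient still in follow-up completes the protocol's follow-up window, dies or is lost to follow-up. This also removes the ambiguity about the last enrolled patient.
- **3.1, Table 1 footnote 21 and 6.1.8.3:** replace the randomization anchor and use one second-malignancy anchor that exists in this trial. The choice is the sponsor's. Treatment discontinuation would shorten footnote 21's window by 30 days, from 395 to 365; the 30-day visit would lengthen Section 6.1.8.3's by the same amount.
- **3.1, duration:** align the 5 years with the 1 year stated elsewhere.
- **7.5.3:** tie the addendum to the redefined study end.

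The cost is a text amendment, plus a database that stays open, and an addendum that waits, until the last window closes. Other sections already call for that follow-up, so no new procedure is added.

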3.2. Rationale for the Study

Pomalidomide is approved for patients with MM who have received at least 2 prior therapies including lenalidomide and bortezomib and have demonstrated disease progression on or within 60 days of completion of the last therapy.[51] Pomalidomide, an analogue of thalidomide, is an immunomodulatory agent with antineoplastic activity. Apoptotic activity and inhibition of proliferation has been observed for pomalidomide in *in vitro* cellular assays using hematopoietic tumor cells. In addition, pomalidomide inhibited the proliferation of lenalidomide-sensitive MM cell lines and synergized with dexamethasone in both lenalidomide-sensitive and lenalidomide-resistant cell lines to induce tumor cell apoptosis. Pomalidomide enhanced T cell- and natural killer (NK) cell-mediated immunity and inhibited production of pro-inflammatory cytokines (e.g., TNF- α and IL-6) by monocytes. Pomalidomide demonstrated anti-angiogenic activity in a mouse tumor model and in the *in vitro* umbilical cord model.[51]

Combination treatment of MM cells with ricolinostat and pomalidomide resulted in synergistic decreases in cellular viability *in vitro*. Time course studies demonstrated accumulation of cell cycle arrest in cells after prolonged exposure to pomalidomide, as well as progressive induction of apoptosis in these cells. Notably, though, combination treatment with ricolinostat plus pomalidomide resulted in synergistic increases in the percentage of MM cells undergoing apoptosis. Furthermore, at the molecular level, MM cells are known to be dependent on expression of the MYC and IRF4 transcription factors. Both ricolinostat and pomalidomide as single agents reduced expression of the critical genes MYC and IRF4, which were reduced even further upon combination treatment.[52, 53]

In vitro data with cultured MM1.S cells demonstrated that the presence of ACY-1215 enhances the activity of lenalidomide in a dose-dependent manner both with and without dexamethasone. Safety data thus far in 15 patients treated with ACY-1215 monotherapy and 46 patients treated with ACY-1215 in combination with dexamethasone and either bortezomib or lenalidomide have shown ACY-1215 to be generally well tolerated and to have a manageable safety profile. Preliminary evidence of anti-tumor activity has been demonstrated in patients treated either with ACY-1215 monotherapy or combination therapy including SD in 6 patients treated with the former regimen. These data, and the potential for reduced side effects with a selective HDAC6 inhibitor with reduced activity against Class I epigenetic HDAC enzymes, support the rationale for clinical investigation of ACY-1215 in combination with pomalidomide/dexamethasone therapy in MM.

3.3. Rationale for the Dose and Schedule Selected

In this study, ACY-1215 will be administered PO for 21 consecutive days for 3 consecutive weeks (Days 1 through 21) with cycles repeating every 28 days in patients with relapsed and/or relapsed-refractory MM. As monotherapy, exposures achieved with 160 mg doses of ACY-1215 were sufficient to increase acetylated tubulin levels by 3-fold in PBMCs (a marker of HDAC6 inhibition) in 3 of 3 patients per dose cohort. Accordingly, a 160 mg dose is likely to be a biologically relevant dose. The initial dose and schedule of ACY-1215 to be administered in this study is based on a dose and schedule equivalent to that established in Study ACE-MM-101, which is evaluating ACY-1215 in combination with lenalidomide and dexamethasone. In the ACE-MM-101 study, ACY-1215 is well-tolerated in combination with lenalidomide with no DLTs or ACY-1215 related Grade 3 or 4 toxicities when administered at 160 mg for 5 out of 7 days for 2 weeks of a 28-day cycle. Dose escalation is ongoing in both magnitude and duration of dose administration.

Based on findings from the Phase 1 segment of the study and as recommended by the SRC, the ACY-1215 dose and schedule to be administered in the Phase 2 segment will be 160 mg PO QD on Days 1 to 21 of a 28-day cycle.

